3.10 Patient consent

Wherever possible informed consent will be obtained from patients prior to randomisation (Appendix 5). It is recognised that in the majority of cases the patients will be unable to give informed consent due to alterations in conscious level caused by illness and therapeutic sedation. In these cases consent will be obtained in line with the legal requirements for each country (see Appendices 6-8)

3.11 Clinical management of the 'early' tracheostomy arm

Patients allocated to this arm will have either a percutaneous or surgical tracheostomy at any time during day 1 to day 4 following ICU admission. The technique for tracheostomy will be determined by local practice and will be recorded. Immediate adverse events will be recorded.

3.12 Clinical management of the 'late' tracheostomy arm

Patients allocated to this arm should not have a tracheostomy before day 10 following ICU admission.

The clinician responsible for their care will review their need for a tracheostomy at day 10, when either of the following strategies may be followed:

- (a) a percutaneous or surgical tracheostomy is performed on or after day 10

or

- (b) no tracheostomy is carried out as it is no longer appropriate to do so (or the patient is no longer in ICU).

3.13 Tracheostomy procedure type

The trial will enrol centres where percutaneous and/or surgical tracheostomies are carried out, according to local current standard practice. The responsible ICU consultant will make all non-protocol management decisions, including the selection of the appropriate procedure for tracheostomy. The mode of ventilation and weaning from ventilatory support will not be protocolised.

3.14 Proposed duration of treatment

A tracheostomy will stay in-situ until decannulation is considered clinically appropriate by the primary caring team.

3.15 Risks associated with the trial

The trial is evaluating the best *time* to perform a tracheostomy. The possible risks related to the timing of tracheostomy are essentially represented by the outcome measures of the trial as no hard evidence is available. The risks related to the tracheostomy procedure itself are the same whether the patient takes part in the trial or has a tracheostomy outside of the trial.

3.16 Adverse Events

As tracheostomy is standard practice in the ICU there are no anticipated complications of tracheostomy associated with the TracMan trial itself. Nevertheless the local research team shall record all complications on the appropriate Case Report Form. The Principal Investigator will report any serious, unanticipated adverse events occurring during the investigation to Dr [name] within 3 working days: [name], TracMan Trial Office, Kadoorie Centre for Critical Care Research and Education, John Radcliffe Hospital, [name]. [contact], Email: [contact].

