The other reason not to undertake a tracheostomy/no tracheostomy trial is that the limited evidence available to date suggests there may be a benefit from *earlier* (and hence increased) use of tracheostomy compared with current practice. The consensus conference in 1989 recommended that tracheostomies should be placed in patients who still require artificial ventilation 10 days after admission to an ICU. There still appears to be a general compliance with this recommendation. Both the literature review undertaken to inform this protocol design and data from a detailed audit of Scottish ICUs (see page 10) suggest that on average tracheostomies are placed on day 10-11 of ventilatory support. However, there are now some limited data to suggest that earlier placement of tracheostomy might improve outcome in critically ill patients. The two most recent trials, and the only two that are methodologically sound^{11,12}, provided conflicting results. In patients with burns Saffle and colleagues showed no advantage to early tracheostomy, whilst Rumbak and colleagues halved the mortality rate and markedly reduced the ICU length of stay in patients in a medical ICU with early tracheostomy. Although the latter supports the use of early tracheostomy, it was a small, US, single centre study involving only medical patients, predominantly with acute or chronic respiratory conditions. The results may not be generalisable to the UK ICU population.

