3.3 The intervention

This trial is not introducing a new procedure but will be evaluating the *timing* of tracheostomy. Specifically:

“Early” tracheostomy:
Tracheostomy to be performed on day 1-4 post admission to ICU

Compared with

“Late” tracheostomy:
No tracheostomy before day 10 post admission to ICU

There is no “usual treatment” arm *per se* as we identified a wide spread of tracheostomy timings in the literature and in the SICSAG audit data. However both of these sources of data suggested that tracheostomies are most commonly placed on day 10-11 following ICU admission. Therefore the timing of tracheostomy placement in the “late” tracheostomy group has been set at day 10 or later to reflect average “usual treatment”.

There will be a number of patients in whom either a tracheostomy will not be required on day 10, either because ventilatory support is no longer needed or the clinicians are reasonably certain that the patient will only need ventilatory support for a further brief period.

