3.4 Outcome measures

Primary outcome measure: Mortality 30 days after randomisation.

Secondary outcome measures: Mortality rate at discharge from hospital
ICU length of stay
Hospital length of stay
Mortality rate at (first) discharge from ICU
Number of days receiving sedative medication
Number of antibiotic-free days.

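### Sections 3.15 and 3.16 say the trial brings no tracheostomy complications of its own and that the outcomes cover timing risk, but early allocation adds procedures and no listed outcome counts their other non-fatal complications

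*Protocol*

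**What the plan says.** Protocol 3.16 (Adverse Events) opens: "As tracheostomy is standard practice in the ICU there are no anticipated complications of tracheostomy associated with the TracMan trial itself". It then requires all complications to be recorded on the case report form.

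Protocol 3.15 (Risks associated with the trial) makes two further statements. On timing: "The possible risks related to the timing of tracheostomy are essentially represented by the outcome measures of the trial". On the procedure itself, it says the risks "are the same whether the patient takes part in the trial or has a tracheostomy outside of the trial".

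Other sections bear on whether these statements can be true:

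- Section 2.1.2 refers to possible benefit from earlier ("and hence increased) use of tracheostomy compared with current practice".
- Section 3.11 has every patient allocated to the early arm undergo a percutaneous or surgical tracheostomy on days 1 to 4.
- Section 3.3 says the late-arm timing "has been set at day 10 or later to reflect average" usual treatment, and adds: "There will be a number of patients in whom either a tracheostomy will not be required on day 10".
- Section 3.12(b) allows that "no tracheostomy is carried out as it is no longer appropriate to do so", or that the patient has already left the ICU.
- Section 3.23 makes two subgroup analyses conditional on enough late-arm patients having a tracheostomy.
- Section 3.4 lists 30-day mortality as primary. The secondary list begins "Secondary outcome measures: Mortality rate at discharge from hospital" and continues with ICU and hospital stay, ICU mortality, days of sedation and antibiotic-free days.

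**The concern.** The sentence in 3.16 is true only if allocation does not change how many patients undergo the procedure. The design makes the number differ between arms. The complications of the added tracheostomies are then a consequence of allocation, so they are a risk of taking part.

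The comparison in 3.15 with a tracheostomy outside the trial is correct per procedure. It does not apply to a patient who, under late allocation or usual care, would have had no tracheostomy.

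The other claim in 3.15, that the outcomes carry the timing risk, is only partly met by the list in 3.4. If 30-day mortality turns out similar, that list can credit an early policy with fewer sedation days or a shorter stay. One part of its cost, non-fatal procedural harm outside the listed measures, has no place there.

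**Working it through.** **Step 1. Does allocation change the number of procedures?**

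| Arm | Tracheostomy under the protocol | Source |
|---|---|---|
| Early | All allocated patients | 3.11 |
| Late | Only if still appropriate on or after day 10 | 3.3, 3.12 |

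Section 2.1.2 says the same in words (earlier means more), and 3.23 allows for the late arm having too few for some analyses. The direction is therefore the protocol's own. It conflicts with 3.16 whatever the exact number.

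**Step 2. What would the outcomes in 3.4 show?**

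| Type of procedural harm | Seen in 3.4? |
|---|---|
| Fatal | Yes, in the mortality outcomes |
| Prolongs ICU or hospital stay | Yes, in length of stay |
| Infection treated with antibiotics | Yes, in antibiotic-free days |
| Other non-fatal complications | No |

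**Step 3. How many extra procedures?** The protocol gives no figure, so there is none to reproduce. The arm size does reproduce closely: 30% against 23.7%, two-sided 0.05, 80% power and a continuity correction give 808 per arm; 808/(1 - 0.024) = 828; 828/(1 - 0.02) = 845, against the stated 846.

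Extra tracheostomies = 846 x (early uptake - late rate). Early uptake of 100% follows 3.11 to the letter; 90% is an assumption. The late rates are:

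- 80%: assumed, because section 3.7 enrols only patients being considered for a tracheostomy.
- 50%: 20 of 40 in the 1984 quasi-randomised trauma trial (Appendix 1).
- 42%: long-stay patients in the North Thames database (3.21).
- 38.5%: 10 of 26 in the 1976 quasi-randomised trial (Appendix 1). The table prints 19%, which is 10/52; the late arm had 26 patients.

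| Late rate | Uptake 100% | Uptake 90% |
|---|---|---|
| 80% | 846 x 0.20 = 169 | 846 x 0.10 = 85 |
| 50% | 846 x 0.50 = 423 | 846 x 0.40 = 338 |
| 42% | 846 x 0.58 = 491 | 846 x 0.48 = 406 |
| 10/26 | 846 x 0.615 = 521 | 846 x 0.515 = 436 |

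Taking the printed 19% at face value would give 846 x 0.81 = 685 at full uptake.

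**Step 4. Is the missed harm fatal or non-fatal?** Appendix 3 gives an unweighted mean operative mortality of 0.3%. Applied to 85 to 521 extra procedures, that is 85 x 0.003 = 0.3 to 521 x 0.003 = 1.6 deaths, which the mortality outcomes would count anyway. The protocol gives no overall non-fatal complication rate. Each percentage point of such a rate would mean between 0.01 x 85 = 0.9 and 0.01 x 521 = 5.2 more early-arm patients affected.

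**The case against.** The strongest reply is that safety is not neglected. Immediate adverse events are recorded (3.11), all complications go on the case report form, and serious unanticipated events are reported within three working days (3.16). The DMEC Chair reviews procedure-related complications once 50 patients are randomised, the committee may ask for any other analysis, and it meets annually (3.34.1, items 1, 5 and 6). All of this stands: neither data collection nor the DMEC text is at fault.

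A second reply is that a complication table by arm commonly belongs in the statistical analysis plan, which is not at hand. That is fair for the table's layout and methods. It does not rescue the risk statement, which is protocol text, nor the claim that the outcomes listed in the protocol already carry the risk.

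Third, 3.15 is hedged, says hard evidence is lacking, and is right per procedure; section 2.1.2 also discusses procedural risk openly. This softens the point but does not remove the conflict with the arm definitions.

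Three stronger readings are tempting and are not supported:

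- **That the protocol implies 423 to 521 extra procedures.** It states only the direction. That band assumes full early uptake and rests on two old quasi-randomised trials that the authors did not count as methodologically sound, plus a long-stay cohort not selected for tracheostomy. Higher late rates are plausible and bring the figure down to 169 or 85.
- **That extra procedures can be set against deaths averted as a ratio.** Such a ratio inherits the same uncertain numerator and assumes the planned effect is real.
- **That those who consent for patients are misled.** They receive information sheets that are not available here, so whether those repeat this wording is unknown.

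**Conclusion.** The point holds in a limited form. Sections 3.15 and 3.16 claim a property that the design does not have: early allocation will give some patients a tracheostomy they would otherwise not have had, and the outcome list omits non-fatal procedural complications that neither prolong stay nor lead to antibiotic treatment. This conclusion rests on the protocol's wording alone and needs no assumed rate.

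The size is uncertain. About 85 to 521 extra procedures among 846 early-arm patients is an illustration over assumed uptake (90% to 100%) and late rates (10/26 to 80%), and the number harmed cannot be estimated from the document. The primary outcome, sample size and type I error are untouched. The point is minor to moderate, and worth acting on because the correction is cheap.

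**What to change.** 1. Reword 3.15 and 3.16 to say that early allocation will lead to a tracheostomy in some patients who would not otherwise have had one, and that the complications of those procedures are a risk of the trial.
2. Add to 3.4 a safety outcome by allocated arm, with all randomised patients as denominator: the proportion receiving a tracheostomy and the proportion with any procedure-related complication.

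The cost is a few sentences in 3.15 and 3.16, a short addition to 3.4 and one table. Complications and tracheostomy technique are already recorded under 3.11 and 3.16, so no new data item is needed. The DMEC procedures need no change.

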3.17 Patients not in the trial

Brief details of patients assessed on Day 1-4 but not in the trial will be recorded on a Patient Screening Log (Appendix 11), at each collaborating unit. Recording this information is to establish an unbiased case selection and full reporting according to the CONSORT statement^{29, 30}.

3.18 Data collection

Clinical data will be collected in a standardised way on a trial specific data form as detailed overleaf. Copies will be retained at the recruiting centre. Data will be transcribed from the patient's notes or the clinical information system (CIS) by the team responsible for the patients' care.

Units collaborating in TracMan and also participating in the Intensive Care National Audit and Research Centre (ICNARC) Case Mix Programme (CMP) will only be required to complete part of the dataset requested on the TracMan trial datasheet. This is because common data (eg admission APACHE II score, hospital mortality etc) are collected by the CMP and the sharing of such data will reduce the data collection burden for collaborating units and avoiding repetition.

Once the TracMan trial datasheet arrives in the trial office in Oxford, the unique CMP identifier recorded will enable the trial office to request appropriate data from the CMP in London. The TracMan trial statistician is based at ICNARC where the CMP data is based. The data will be transferred electronically to Oxford, or will be personally handed over on disc (encrypted).

We predict over half the ICUs recruited to the trial will be participants in the CMP. ICNARC will obtain signed agreement in advance from collaborating units to share this anonymised data with TracMan. This approach has been used in the PAC-Man trial and works well.

The CMP database has extensive data validation checks in place.

Before the study starts, data collection forms will be piloted to determine ease of use, inter-rater variability and other practical issues by collecting data on patients routinely treated with and without tracheostomies on the Adult ICU at Oxford and one other test site.

Data are collected for the period of the patient's stay in ICU. The hospital discharge date will be obtained from the local patient administration system. When a patient is transferred to another acute hospital, the discharge date will be requested from the receiving hospital. However for some patients it may be necessary to contact the patient's general practitioner to obtain the patients status.

Patients will be 'flagged' on the Office of National Statistics (ONS) database to ensure reliable collection of the primary outcome measure (patient status 30 days after randomisation). Patients alive at day 30 will be followed up for two years on the ONS database.

3.19 Sample size

The planned sample size is 1692 patients (846 in each arm).

[figure not shown]
3.20 Justification for sample size and details of the power calculation

The sample size calculations are based on the primary outcome measure, 30 day mortality. There are no data available in the UK on 30 day mortality in critically ill patients receiving tracheostomies so we used hospital mortality as a surrogate for 30 day mortality. There are a number of estimates of hospital mortality in tracheostomised patients on which to base the calculations.

The survey of 35 UK ICUs gave a mean value of 21 per cent for ICU mortality for tracheostomised patients. Hospital mortality is invariably higher than ICU mortality³¹, the mean increase in mortality between ICU and hospital discharge in the UK is 9.3 per cent absolute. Thus the predicted hospital mortality for these tracheostomised patients would be slightly over 30 per cent. This is very close to the UK average hospital mortality for all ICU admissions of 30.8 per cent³¹.

A meta-analysis carried out in 2005 of four methodologically sound published trials of tracheostomy timing show a relative risk reduction of 21 per cent.

Figure 2: Forest plot showing random effects meta-analysis of relative risk (95% confidence interval) of mortality with early compared with late tracheostomy.

We therefore selected a 21 per cent relative reduction in mortality as the clinically significant difference we wished our trial to detect.

Using a difference in hospital mortality of 21 per cent relative, 6.3 per cent absolute, with a predicted mortality in the “late” arm of 30 per cent, with an 80 per cent certainty of detecting a real difference and an alpha value of 0.05 the calculated sample size with a continuity correction is 1616 patients (808 in each arm).

In a recently completed multicentre study of pulmonary artery catheters in ICU patients (PAC-Man), 2.4 per cent of recruited patients or their relatives subsequently withdrew their consent, or were randomised in error. A similar dropout rate in this study would require a total of 828 patients per arm (1656 total). In addition there will be a cross-over rate, again using PAC-Man data we estimate this to be 2 per cent in the late arm. This gives a required sample size of 846 patients per arm (1692 total). This value has been chosen as the sample size for the trial.

We have reviewed the effects that differing estimates of hospital mortality might have on the power of the study. The absolute difference detectable at the same power is slightly higher (i.e. the trial would be less sensitive) if the true mortality in the late arm exceeds that predicted, but would be lower if the true late mortality is less than that predicted. Table 1 below summarises the effects of differing estimates of hospital mortality would have on the power of the study assuming the same sample size and levels of certainty.

A study size of 1692 patients will allow a difference of less than one day in the secondary outcomes of length of ICU and hospital stay to be detected. Data are not available to estimate the power to detect changes in antibiotic use and sedative use.

Table 1: Hospital mortality estimates

Source of estimate	Hospital mortality (%)	Relative mortality reduction detectable	Absolute mortality reduction detectable
Lowest value from survey of UK ICUs	9%	42.2%	3.8%
Highest value from survey of UK ICUs	58%	12.2%	7.1%
Literature review	38.1%	17.8%	6.8%
SICS audit	8%	43.8%	3.5%

Should the TracMan trial obtain further funding, it could be extended to both increase the certainty of detecting a 21 per cent relative reduction in mortality, and increase the chances of detecting a lesser treatment effect. Table 2 below gives the sample size required to detect a 21 per cent relative reduction in mortality from a control group mortality of 30 per cent for a power of 90 per cent, 95 per cent, and 99 per cent.

Table 2: Sample size calculations

Power	Total sample size with continuity correction	Sample size allowing for crossovers and dropouts
80%	1616	1692
90%	2140	2284
95%	2630	2806
99%	3690	3938

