3.22 Type of analysis

The principal comparisons will be between those allocated to “early” tracheostomy and those allocated to “late” tracheostomy (the “intention to treat” principle). The primary outcome variable will be proportion of patients surviving to 30 days post randomisation in each arm which will be compared using Fisher’s exact test.

Hospital and ICU mortality will also be compared between arms using Fisher’s exact test. The survival curves for the two arms will be calculated using the Kaplan-Meier method, with the starting time being the time of randomisation, and compared using a log-rank test. Differences in length of ICU stay, hospital stay, number of days sedated and number of antibiotic-free days between arms will be tested using the Wilcoxon rank-sum test.

Mr [name], Senior Statistician at ICNARC, will act as trial statistician and perform the analyses.

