ICU LOS early arm (days)	Mean 4.8 SD 1.4	Not stated	Mean 20 SD 2	Mean 16 SD 1	Not stated	Not stated	Not stated
ICU LOS late arm (days)	Mean 16.2 SD 3.8	Not stated	Mean 24 SD 2	Mean 37 SD 4	Not stated	Not stated	Not stated
Hospital LOS early arm (days)	Not stated	Mean 58.4 SD 6.3 Range 14-124	Not stated	Mean 34 SD 4	Not stated	Not stated	Not stated
Hospital LOS late arm (days)	Not stated	Mean 57.3 SD 8.0 Range 11-153	Not stated	Mean 51 SD 4	Not stated	Not stated	Not stated
Patients developing pneumonia, early arm	3 (5%)	21 (100%)	26 (49%)	25* (50%)	20 (59%)	Not stated	Not stated
Patients developing pneumonia, late arm	15 (25%)	22 (96%)	32 (57%)	47* (85%)	20 (50%)	Not stated	Not stated
Late arm patients receiving tracheostomy	Not stated	Not stated	Not stated	Not stated	20 (50%)	Not stated	10 (19%)
Other outcomes	Laryngeal trauma equal in arms	1/21 (4.8%) decannulated by 14 days in early arm, 7/23 (30%) decannulated by 14 days in late arm	None stated	None stated	None stated	None stated	None stated
Comments	* = 30 day mortality	Mortality assumed to be hospital mortality	Additional group recruited on day 10-14 post injury, not included in this summary. Mortality assumed to be hospital mortality.	* = Calculated values not reported in the original publication	* = Text is ambiguous, elsewhere ventilated > 7 days is given as an inclusion criterion.	No data on outcome by group in paper	No data on outcome by group in paper

Literature search: Tracheostomy retrospective chart reviews/prospective observational studies

APPENDIX 2

Authors	Teoh et al ¹⁹	Brook et al ²⁰	Armstrong et al ²⁴	Blot et al ²¹	D'Amelio et al ²²	Lesnik et al ²³
Publication year	2001	2000	1998	1995	1994	1992
Patient population	30 neurosurgical patients	90 patients in medical ICU	157 blunt trauma patients	53 neutropaenic patients	31 head injured patients	101 blunt trauma patients
Setting	Single neurosurgical unit, Singapore	Single medical ICU, USA	Single hospital, USA	Single ICU, France	Single neurosurgical unit, USA	Single hospital, USA
Age limits	Not stated	>17 years	Not stated	Not stated	Not stated	Not stated
Exclusions	Percutaneous tracheostomy	Transfers from other ICUs	Patients with craniofacial injuries	Not stated	Open gastrostomy*	Patients with craniofacial injuries

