Early group definition	Tracheostomy before or on day 7	Tracheostomy before or on day 10 of mechanical ventilation	Tracheostomy before or on day 6 of mechanical ventilation	Tracheostomy before or on day 2	Tracheostomy before or on day 7	Tracheostomy before or on day 4
Late group definition	Tracheostomy after day 7	Tracheostomy after day 10	Tracheostomy after day 6	Tracheostomy after day 2	Tracheostomy after day 7	Tracheostomy after day 4
Tracheostomy technique	Surgical	Not stated	Not stated	Surgical	Percutaneous and surgical	Surgical (implied not stated)
Early/late n	12/18	53/37	62/95	20/33	21/10	32/69
ICU mortality early group	Not stated	Not stated	Not stated	14 (70%)	Not stated	Not stated
ICU mortality late group	Not stated	Not stated	Not stated	26 (79%)	Not stated	Not stated
Hospital mortality early group	Not stated	15 (28%)	7 (11.3%)	15 (75%)	2 (10%)	Not stated
Hospital mortality late group	Not stated	14 (37.8%)	11 (11.6%)	27 (82%)	1 (10%)	Not stated
ICU LOS early group (days)	Not stated	Mean 15.6 SD 9.3	Mean 15 SD 12	Mean 28 SD 24	Mean 12.6 SD not stated	Not stated
ICU LOS late group (days)	Not stated	Mean 29.3 SD 15.4	Mean 29 SD 26	Mean 19 SD 18	Mean 26.2 SD not stated	Not stated
Hospital LOS early group (days)	Not stated	Mean 44.8 SD 30.3	Mean 33 SD 24	Mean 31 SD 26	Not stated	Not stated
Hospital LOS late group (days)	Not stated	Mean 49.6 SD 22.3	Mean 68 SD 48	Mean 23 SD 21	Not stated	Not stated
Patients developing pneumonia, early group	Not stated	16 (30%)	Not stated	2 (10%)	Not stated	6 (19%)
Patients developing pneumonia, late group	Not stated	16 (43.2%)	Not stated	3 (9%)	Not stated	41 (59%)
Comments					* = All patients also had a percutaneous gastrostomy	

Literature search: Data to inform the protocol development and power calculations

APPENDIX 3

Section 1 of table

Reference number	Study type	Study topic	Year of publication	First author surname	Country	n Tracheostomy patients	Patient group
³⁵	Prospective case series	Single dilator technique	2003	Westphal	Germany	10	Long term ventilation patients
³⁶	Prospective case series	Complications of tracheostomy in ICU	2003	Francois	France	118	Mixed medical/surgical ICU patients
³⁷	Prospective case series	PDT	2003	Polderman	Netherlands	211	Mixed medical/surgical ICU patients
³⁸	Prospective case series	Nosocomial pneumonia in ICU patients with PDT	2003	Rello	Spain	110	Mixed medical/surgical ICU patients

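### The claim that 1692 patients can detect a difference of under one day in stay is contradicted by the protocol's own data for hospital stay, and unsupported for ICU stay

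*Protocol*

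**What the plan says.** Section 3.19: "The planned sample size is 1692 patients (846 in each arm"). Section 3.20 derives this from 30-day mortality, "with an 80 per cent certainty of detecting a real difference and an alpha value of 0.05", and states that "the calculated sample size with a continuity correction is 1616 patients (808 in each arm") before allowance for dropout and crossover.

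The same section then adds that a study of this size "will allow a difference of less than one day in the secondary outcomes of length of ICU and hospital stay to be detected". No SD, power, test or reference comes with that sentence. Section 3.22 says that differences in length of stay "between arms will be tested using the Wilcoxon rank-sum test".

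The SDs of stay that the protocol holds are in its literature appendices:
- **Appendix 1 (trials):** ICU stay 1 to 4 days; hospital stay 4 to 8 days. The burns trial's early arm reads "Mean 58.4 SD 6.3", with a range of 14 to 124 days.
- **Appendix 2 (observational studies):** ICU stay 9.3 to 26 days, for example "Mean 29.3 SD 15.4"; hospital stay 21 to 48 days, for example "Mean 44.8 SD 30.3".
- **Appendix 3 (case series):** ICU stay only, with SDs that include 5.3, 15.5, 23 and 50 days.

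Section 2.3.2 reports that hospital stay was too rarely given in the wider search to yield useful data.

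**The concern.** The sentence states a definite sensitivity for two listed secondary outcomes. Stay in critically ill patients is long and skewed, and the Appendix 2 SDs are several times larger than a one-day detectable difference can tolerate at this sample size. The SDs that would fit come mainly from Appendix 1, and at least one pair of those cannot be SDs of the data shown beside them.

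If the sentence stands, the protocol credits the trial with a precision on hospital stay that its own figures do not support. A reader of a neutral result could then suppose that a difference of a day or more would have been found, when differences of several days may remain compatible with the data.

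**Working it through.** **1. Settings.** For 30% against 23.7% mortality, two-sided alpha 0.05 and 80% power, the standard two-proportion formula gives 776 per arm. With the continuity correction it gives 808 per arm, 1616 in total, which is the protocol's figure. Sidedness is not stated, but the two-sided reading reproduces 1616 exactly, so it is used below.

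**2. Formula.** Detectable difference in means = (1.960 + 0.842) × √[(SD₁² + SD₂²)/n], with n = 846 per arm. With equal SDs this is 2.802 × SD × √(2/846) = 0.136 × SD. A result below one day needs SD < 1/0.136, about 7.3 days (7.2 with 808 per arm).

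**3. Results from the listed SDs**

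| Source | Outcome | SDs (days) | Detectable difference (days) |
|---|---|---|---|
| App. 1 medical ICU trial (ref 11) | ICU | 1.4 / 3.8 | 0.39 |
| App. 1 trauma trial (ref 17) | ICU | 2 / 2 | 0.27 |
| App. 1 surgical ICU trial (ref 18) | ICU | 1 / 4 | 0.40 |
| App. 2 medical ICU cohort (ref 20) | ICU | 9.3 / 15.4 | 1.73 |
| App. 2 blunt trauma cohort (ref 24) | ICU | 12 / 26 | 2.76 |
| App. 2 neutropaenic cohort (ref 21) | ICU | 24 / 18 | 2.89 |
| App. 3 series (ref 37) | ICU | 5.3 | 0.72 |
| App. 3 series (ref 99) | ICU | 50 | 6.81 |
| App. 1 burns trial (ref 12) | Hospital | 6.3 / 8.0 | 0.98 |
| App. 1 surgical ICU trial (ref 18) | Hospital | 4 / 4 | 0.54 |
| App. 2 medical ICU cohort (ref 20) | Hospital | 30.3 / 22.3 | 3.62 |
| App. 2 blunt trauma cohort (ref 24) | Hospital | 24 / 48 | 5.17 |
| App. 2 neutropaenic cohort (ref 21) | Hospital | 26 / 21 | 3.22 |

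On the Appendix 2 SDs, power for a true one-day difference in means is 16 to 37% for ICU stay and 8 to 14% for hospital stay.

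**4. Are the small hospital-stay SDs possible?** For n values with range R, the smallest possible SD puts one value at each end and the rest at the midpoint: R/√[2(n − 1)].
- Burns trial, early arm: n = 21, R = 124 − 14 = 110, so SD ≥ 110/√40 = 17.4. Listed: 6.3.
- Burns trial, late arm: n = 23, R = 153 − 11 = 142, so SD ≥ 142/√44 = 21.4. Listed: 8.0.

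The listed SDs and ranges cannot both be right. Read as standard errors, the values imply SDs of 6.3√21 = 28.9 and 8.0√23 = 38.4, and a detectable difference of 4.6 days.

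The surgical ICU trial lists a hospital-stay SD of 4 around means of 34 and 51 days, which is implausibly tight. The same trial's late-arm ICU SD is 4 in Appendix 1 but 1 in Appendix 3. Read as standard errors (n = 51 and 55), its hospital values give SDs of 28.6 and 29.7 and a detectable difference of 4.0 days.

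**5. More lenient readings, on the Appendix 2 SDs**
- One-sided 5%, 80% power: ICU 1.5 to 2.6 days; hospital 2.9 to 4.6.
- Two-sided 5%, only 50% power: ICU 1.2 to 2.0 days; hospital 2.2 to 3.6.
- Wilcoxon test at 80% power, by simulation. Lognormal data are an assumption; means and SDs are those of single Appendix 2 groups; results carry simulation error of 0.1 to 0.2 day. ICU: about 1.0 to 2.1 days for a pure shift and 1.2 to 2.8 for a proportional change. Hospital: about 1.6 to 4.4 and 2.4 to 5.9.
- Simulated Wilcoxon power for a one-day difference: 16 to 84% for ICU stay (84% only with mean 15.6, SD 9.3 and a pure shift); 8 to 42% for hospital stay.

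**The case against.** The strongest case on the other side concerns ICU stay. The listed ICU SDs run from 1 to 50 days, and several give less than one day. The medical ICU trial's 1.4 and 3.8 cannot be shown from the protocol to be anything but SDs. One Appendix 3 series has an SD of 5.3, although its mean stay of 6.1 days is far below the 20-day average in section 2.3.2. The Appendix 2 studies are small cohorts in mixed populations, and section 2.3.1 itself declines to draw conclusions from them about timing. The planned test is a rank test, which can be more sensitive than a comparison of means on skewed data, and two Appendix 2 inputs (15.6/9.3 and 15/12) bring it to about one day under a pure shift. All of this stands. A reader might infer that the ICU figure is wrong by two to five fold; the documents do not support a fixed factor there.

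A reader might also infer that the authors took standard errors for SDs and that this produced the claim. The burns trial's face values do give 0.98 day, but other listed pairs give 0.27 to 0.54 day, and the protocol does not say which SD was used. Mislabelling is the likely explanation for the burns trial, plausible for the trauma and surgical trials, and not shown for the medical ICU trial. The range bound proves an inconsistency; only the source paper can show which number is wrong.

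None of this rescues hospital stay. No credible listed SD, lenient alpha, lower power or rank-test simulation reaches one day.

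**Conclusion.** The sentence is wrong as written. For hospital stay it conflicts with the protocol's own data: about 3 to 5 days is detectable on a comparison of means, and about 1.6 to 5.9 days under the planned Wilcoxon test across the simulated inputs. For ICU stay it is unsupported: about 1.7 to 2.9 days on a comparison of means, approaching one day only with favourable skewed inputs and a pure shift.

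These sizes assume 846 analysable patients per arm, two-sided 5%, 80% power and SDs like those in Appendix 2; the rank-test figures also assume lognormal stay. The conclusion for hospital stay does not hinge on any one of these choices; the exact ICU figure does.

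The point is limited to a descriptive statement about secondary outcomes. It drives no sample size, test or stopping rule. The mortality calculation reproduces and is unchanged.

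**What to change.** Either delete the sentence in section 3.20, or replace it with detectable differences that name the SD source, power and test. For example: *On the SDs in Appendix 2, with 80% power, two-sided 5% significance and a comparison of means, the trial can detect differences of about 2 to 3 days in ICU stay and 3 to 5 days in hospital stay; the planned Wilcoxon test may be somewhat more sensitive.*

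Check the burns trial's hospital-stay SDs in Appendix 1 against the source paper, and likewise the other Appendix 1 SDs of 1 to 4 days, before using any of them. Reconcile the surgical ICU trial's late-arm ICU SD, which differs between Appendices 1 and 3.

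The cost is wording and a source check. The stated sensitivity becomes less favourable; the design, sample size and analysis do not change.
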